10.3.1.2 Criteria for the Calculation of an Apparent Terminal Phase Half-Life

- **Number of Data Points**

- At least 3 data points will be included in the regression analysis and preferably should not include C_{\max} .

- **Goodness of Fit**

- When assessing terminal phases, the R^2 adjusted value will be used as a measure of the goodness of fit of the data points to the determined line.
- An terminal phase half-life will only be calculated if the R^2 adjusted value of the regression line is greater than or equal to 0.7.

- **Period of Estimation**

- Time period used for the estimation of apparent terminal phase half-lives, where possible, will be over at least 2 half-lives.
- Where an elimination half-life is estimated over a time period of less than 2 half-lives, it will be flagged in the data listings at the discretion of the Pharmacokineticist, and the robustness of the value should be discussed in the study report.

- **Calculation of AUC**

- The minimum requirement for the calculation of AUC will be the inclusion of at least 3 consecutive plasma concentrations above the lower limit of quantification (LLOQ), with at least 1 of these concentrations following C_{\max} . Exceptions may be made for metabolites.
- For any partial AUC determination (ie, AUC_{0-12} and AUC_{0-24}), nominal time will generally be used for the end of the interval. Actual times for partial AUC intervals may be used at the discretion of the Pharmacokineticist.

- $AUC_{0-\infty}$ values where the percentage extrapolation is less than 20% will be reported. $AUC_{0-\infty}$ values where the percentage extrapolation is 20% to 30% will be flagged and included in the descriptive statistics, whilst $AUC_{0-\infty}$ values where the percentage extrapolation is greater than 30% will be reported but excluded from descriptive statistics.

- **Anomalous Values**

- If a value is considered to be anomalous due to being inconsistent with the expected PK profile, it may be appropriate to exclude this point from the PK analysis based on the Covance SOP. However, the exclusion of data must have strong justification and will be documented in the raw data and study report.
- Positive predose value(s) greater than 5% of C_{max} may be excluded from the summary statistics of PK tables and statistical analysis at the discretion of the Pharmacokineticist and BioMed Valley Discoveries Inc.

10.3.2 Presentation of Pharmacokinetic Data

10.3.2.1 Presentation of Pharmacokinetic Plasma Drug Concentration Data

The following rules will be applied if there are values that are BLOQ or if there are missing values (eg, no result [NR]) in a plasma concentration data series to be summarized.

- For the calculation of summary statistics, BLOQ values will be set to zero.
- If an embedded BLOQ value is considered anomalous within the concentration-time profile, this value will be excluded from the summary statistics.
- Where there is NR, these will be set to missing.
- If there are less than 3 values in the data series, only the min, max, and n will be presented. The other summary statistics will be denoted as not calculated (NC). BLOQ is considered a value.
- If all the values are BLOQ, then the arithmetic mean, arithmetic SD, median, min, and max will be presented as zero.

- If the value of the arithmetic mean or median is below the LLOQ, these values will be presented as zero.

10.3.2.2 Presentation of Pharmacokinetic Parameters

- For the calculation of summary statistics of PK parameters, all NR and NC values in a data series will be set to missing.
- The AUC values will be set to NC if they have been calculated using fewer than 3 concentrations, and/or 3 concentrations if the last is C_{\max} (exception made for metabolites).

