5 SUBJECT SELECTION

Subjects who meet all the inclusion criteria and for whom none of the exclusion criteria apply will be eligible to be enrolled into the study. Safety evaluations may be repeated at the Investigator's (or designee's) discretion.

Six subjects will be enrolled to have at least 4 subjects complete the study.

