8. SAMPLE SIZE JUSTIFICATION

The sample size chosen for this study was based on precedent set by other PK studies of similar nature and was not based on power calculations. No formal statistical hypotheses are planned to be tested in this study.

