10. STATISTICAL METHODOLOGY

10.1 GENERAL

Data listings will be provided for the All Subjects Population. Summary statistics and statistical analyses will be performed for subjects included in the relevant analysis populations (Safety/PK).

For continuous data, summary statistics will include the arithmetic mean, arithmetic standard deviation (SD), median, minimum (min), maximum (max), and number of observations (n). Data listings will be provided for all subjects up to the point of withdrawal, with any subjects excluded from the relevant population highlighted. For the calculation of summary statistics and statistical analysis, unrounded data will be used.

Missing values will not be imputed.

Data analysis will be performed using SAS® Version 9.3 or higher.

Analysis Data Model (ADaM) datasets will be prepared using Clinical Data Interchange Standards Consortium (CDISC) ADaM Version 2.1, and CDISC ADaM Implementation Guide Version 1.1. Pinnacle 21 Community Validator Version 2.2.0 will be utilized to ensure compliance with CDISC standards.

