AUC _{0-∞} Plasma Metabolites/ Total Radioactivity Ratio	AUC _{0-∞} of nonradiolabeled metabolites in plasma/AUC _{0-∞} of total radioactivity in plasma
AUC ₀₋₁₂ Plasma Metabolites/ Total Radioactivity Ratio	AUC ₀₋₁₂ of nonradiolabeled metabolites in plasma/AUC ₀₋₁₂ of total radioactivity in plasma
AUC ₀₋₂₄ Plasma Metabolites/ Total Radioactivity Ratio	AUC ₀₋₂₄ of nonradiolabeled metabolites in plasma/AUC ₀₋₂₄ of total radioactivity in plasma

In addition, the following PK parameters will be calculated, whenever possible, for each subject based on the urine concentrations of BVD-523 and total radioactivity. Parameters for BVD-523 in urine will be calculated and reported by the Covance EC Biometrics PK group; parameters for total radioactivity (except CL_R, which will be calculated for BVD-523 only) will be calculated and reported by the Covance Radioanalysis group. Urinary parameters for total radioactivity will also be presented in the CSR tables.

Parameter	Definition
A_{eu}	amount excreted in urine over sampling interval (t1-t2) where t1 and t2 are the start and end times of the sampling interval, respectively
Cumulative A_{eu}	cumulative amount excreted in urine, calculated as the sum of the amount excreted in urine for each collection interval
CL_R	renal clearance, where $CL_R = A_{eu}/AUC_{0-\infty}$ (for BVD-523 only)
% F_{eu}	percent of dose excreted in urine over sampling interval (t1-t2), where % Excreted = $100 (A_{eu}/\text{dose})$
Cumulative % F_{eu}	cumulative percent of dose excreted in urine, calculated as the sum of the percent of dose excreted in urine for each collection interval

The following PK parameters will be calculated, whenever possible, for each subject based on the fecal concentrations of total radioactivity. Parameters for total radioactivity will be reported by the Covance Radioanalysis group in the Radioanalysis report. Fecal parameters for total radioactivity will also be presented in the CSR tables.

Parameter	Definition
A_{ef}	amount excreted in feces over sampling interval (t1-t2)
Cumulative A_{ef}	cumulative amount excreted in feces, calculated as the sum of the amount excreted in feces for each collection interval
% F_{ef}	percent of dose excreted in feces over sampling interval (t1-t2), where % Excreted = $100 (A_{ef}/\text{dose})$
Cumulative % F_{ef}	cumulative percent of dose excreted in feces, calculated as the sum of the percent of dose excreted in feces for each collection interval

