Additional PK parameters may be determined where appropriate.

Pharmacokinetic analysis will, where possible, be carried out using actual postdose times recorded in the raw data. If actual times are missing, nominal times may be used with sponsor approval.

Concentrations are used as supplied by the analytical laboratory for PK analysis. The units of concentration and resulting PK parameters, with amount or concentration in the unit, will be presented as they are received from the analytical laboratory.

C_{\max} and T_{\max} will be obtained directly from the plasma concentration-time profiles.

For multiple peaks, the highest postdose concentration will be reported as C_{\max} . In the case that multiple peaks are of equal magnitude, the earliest T_{\max} will be reported.

The amount excreted in urine (A_{eu}) for each urine collection interval will be calculated as the product of urine concentration and urine weight; Cumulative A_{eu} 0-x hour will be calculated by summing the A_{eu} values for each collection interval over the 0-x hour period.

In addition to the PK and radioanalysis results, a discussion of the results of metabolite characterization will be included in the CSR however no tables, figures, or listings will be generated. The quantitation of parent and metabolites (concentrations and/or percent of dose), as applicable, other applicable metabolite characterization results (representative chromatograms, proposed metabolite structures, etc.), and any PK parameters calculated from the radiochromatography data will be reported in the Metabolite Profiling and Identification report. Radiochromatography PK parameters may be summarized in the CSR along with PK parameters determined from the bioanalytical data.

10.3.1.1 Criteria For Handling Concentrations below the Limit of Quantification in Pharmacokinetic Analysis

Concentration values that are below the lower level of quantification (BLOQ) will be set to zero, with defined exceptions as follows;

- Any embedded BLOQ value (between 2 quantifiable concentrations) and BLOQ values following the last quantifiable concentration in a profile will be set to missing for the purposes of PK analysis.
- If there are late positive concentration values following 2 BLOQ concentration values in the apparent terminal phase, these values will be evaluated. If these values are considered to be anomalous, they will be set to missing.

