- If an entire concentration-time profile is BLOQ, the profile will be excluded from the PK analysis.
- If a predose concentration is missing, this value may be set to zero with sponsor approval.

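### The SAP's rules for concentrations below quantification are not limited to plasma and blood; applied to urine BVD-523 as written, they drop near-zero excretion and overstate mean amounts and percent of dose.

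*SAP*

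**What the plan says.** SAP 10.3.1 lists the interval and cumulative amounts and percents of dose in urine and feces (A_eu, %F_eu, A_ef, %F_ef) among the PK parameters. The urine amount for an interval is urine concentration times urine weight. Cumulative values are plain sums; for feces, "cumulative percent of dose excreted in feces, calculated as the sum of the percent of dose excreted in feces for each collection interval". BVD-523 in urine is calculated by the biometrics PK group. Total radioactivity in excreta is reported by a separate radioanalysis group and also shown in the CSR tables.

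The rules for low or absent values are these:

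- **Default (SAP 10.3.1.1):** "Concentration values that are below the lower level of quantification (BLOQ) will be set to zero, with defined exceptions as follows".
- **Exception for embedded and trailing values:** both become missing. For the latter, "BLOQ values following the last quantifiable concentration in a profile will be set to missing for the purposes of PK analysis".
- **Exception for a profile with nothing quantifiable:** "If an entire concentration-time profile is BLOQ, the profile will be excluded from the PK analysis".
- **Concentration summaries (SAP 10.3.2.1):** BLOQ counts as zero, but the section covers plasma series only.
- **Parameter summaries (SAP 10.3.2.2):** "For the calculation of summary statistics of PK parameters, all NR and NC values in a data series will be set to missing".
- **General (SAP 10.1):** "Missing values will not be imputed".

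Neither document says how an interval with no stool or no void is coded, or how a cumulative sum treats a missing term.

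**The concern.** The exceptions in SAP 10.3.1.1 suit a plasma curve, where a BLOQ value after the last quantifiable one should not pull the AUC or the terminal slope. Excreta are different. A BLOQ urine concentration means that almost nothing was excreted in that interval. That is a result, and its best value is about zero. Making it missing turns the interval mean into a mean among subjects who were still excreting measurable drug.

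The situation is plausible for urine BVD-523. Protocol 2.1.1 describes mainly hepatic elimination in animals. Protocol 2.1.2 gives a half-life of 9 to 11 hours in patients, while urine is collected to at least 168 hours. Routes of elimination are part of the primary objective, and the tables rest on six subjects and possibly only four completers.

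**Working it through.** The plan gives no recovery figure to reproduce, and its sample size "was not based on power calculations". The check is therefore on what the written rules do.

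**Inputs.** n = 6, or 4 at the planned minimum (Protocol 5: "Six subjects will be enrolled to have at least 4 subjects complete the study"); half-life 9 to 11 h (Protocol 2.1.2); urine intervals 0-6, 6-12, 12-24 h and then every 24 h (Protocol Table 6-1).

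**Step 1: does a urine value reach the missing rule?** A trailing BLOQ urine concentration becomes missing under 10.3.1.1. Concentration times weight then cannot be formed, so A_eu and %F_eu are not calculated. 10.3.2.2 makes them missing in the summary, and 10.1 bars imputation. The BLOQ-to-zero rule in 10.3.2.1 cannot restore them because it covers plasma only.

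**Step 2: will trailing BLOQ values occur?** At 72 h, 72/11 = 6.5 to 72/9 = 8.0 half-lives have passed, so levels are about 2^-6.5 = 1.1% to 2^-8 = 0.4% of their starting point. No urine LLOQ is given, so the first BLOQ interval cannot be predicted, but it need not be the same in every subject.

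**Step 3: effect on an interval mean.** Let S be the total over the n-k quantifiable subjects.

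- BLOQ as zero: mean = S/n
- BLOQ as missing: mean = S/(n-k)
- Ratio = n/(n-k)

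| n | k | Ratio |
|---|---|---|
| 6 | 1 | 6/5 = 1.20 |
| 6 | 2 | 6/4 = 1.50 |
| 6 | 3 | 6/3 = 2.00 |
| 4 | 1 | 4/3 = 1.33 |
| 4 | 2 | 4/2 = 2.00 |

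The ratio is against BLOQ counted as zero. Against the small true amounts it is slightly lower. If all n are BLOQ, no mean appears where zero belongs.

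**Step 4: absolute size.** With m the mean among quantifiable subjects, the overstatement is m - m(n-k)/n = m × k/n. For n = 6 that is 0.17m, 0.33m or 0.50m for k = 1, 2, 3. Where some subjects are BLOQ, m is itself probably small.

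**Step 5: cumulative values.** If missing terms are skipped, a subject's cumulative amount is almost unchanged. Mean cumulative excretion is then (sum of S_j)/n over intervals j, while the interval means add to the sum of S_j/(n-k_j). The two differ as soon as any k_j is above zero. A subject who is BLOQ throughout is removed altogether, so mean cumulative %F_eu and mean renal clearance (A_eu/AUC) also rise by n/(n-k).

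**Step 6: excreta radioactivity, as a risk only.** Suppose intervals with no stool were coded as no result. Take an assumed example of six subjects, seven daily intervals, 60% of dose in feces for each, and six empty subject-intervals:

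- Zeros kept: 4.67, 22.17, 15.50, 9.00, 6.00, 1.83, 0.83; total 60.0.
- Zeros missing: 7.00, 26.60, 18.60, 10.80, 6.00, 1.83, 1.00; total 71.8.
- Mean cumulative recovery stays at 60.0 if missing terms are skipped.

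At assumed, independent no-stool rates of 5%, 10% and 20% per interval, the chance that at least one of six subjects is affected in a given interval is 1-(1-p)^6 = 26%, 47% and 74%. The documents give no such rate.

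**The case against.** The best defence is that the default in 10.3.1.1 is zero, and that its exceptions use the language of concentration-time curves: profile, terminal phase, predose value. If they do not reach excreta, a BLOQ urine interval already counts as zero and nothing is wrong. This is a fair account of what the authors may have meant. It is not what the text limits itself to. 10.3.1.1 sits under the section that defines the excreta parameters, while 10.3.2.1 and the AUC minimum in 10.3.1.2 are expressly confined to plasma. An analyst following the SAP has no stated ground for exempting urine.

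A reader might go further and infer that the SAP turns no-stool days into missing values, overstates radioactivity recovery, or leaves cumulative recovery undefined. The documents do not support that:

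- 10.3.2.2 acts only on values already labelled as no result or not calculated, and nothing gives an empty interval that label.
- The radioanalysis group's conventions and the TFL shells are outside these documents.
- Entry requires at least one bowel movement a day (Protocol 5.1) and the diet is high in fiber (Protocol 6.3.1), although prune juice and laxatives are provided for.
- Early discharge requires at least 90% of dose recovered (Protocol 4.1), so cumulative recovery has to be computed during the study, across any empty intervals.
- The sum of interval means is not a planned statistic.

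It also stands that the study is descriptive and that n is reported with each summary, so dropped values would be visible.

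**Conclusion.** The point holds for BVD-523 in urine. Followed as written, 10.3.1.1 removes near-zero intervals and subjects with no quantifiable urine drug. It overstates mean A_eu and %F_eu by n/(n-k), which is 1.2 to 2.0 times for one to three of six subjects, and it breaks agreement between interval and cumulative tables. This rests on reading the exceptions as covering urine, and on at least one subject, but not all, being BLOQ. The change in percent of dose is probably small; it cannot be computed without an LLOQ.

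For total radioactivity in urine and feces, the SAP leaves a gap that could have the same effect in the CSR tables. That is a risk, and bias in overall recovery is not shown. The point is worth correcting before database lock, but it does not threaten the study's main conclusion.

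**What to change.** Amend SAP 10.3.1.1 and 10.3.2.2 as follows:

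1. Limit the set-to-missing and profile-exclusion rules to plasma and whole-blood profiles.
2. For urine and feces, give an interval with a BLOQ concentration, or with nothing produced, an amount of 0 and 0% of dose.
3. Keep a subject whose urine BVD-523 is BLOQ throughout, with amount 0.
4. Treat as missing, with a flag, only collections that were produced but lost or incomplete.
5. State how a cumulative sum treats a missing term, and apply the same rules to the radioactivity values shown in the CSR tables.

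With zeros kept, the factor in Step 3 is 1.00, and interval means add up to mean cumulative excretion when no collection is lost. The cost is a few SAP sentences and one dataset flag separating nothing produced from sample lost. Counting BLOQ as zero slightly understates excretion, by less than LLOQ times sample weight per interval.

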10.3.3 Pharmacokinetic Statistical Methodology

Descriptive statistics (arithmetic mean, SD, median, min, max, and number of observations) will be calculated for the PK parameters. No formal statistical analyses are planned.

10.4 Safety and Tolerability Assessments

10.4.1 Adverse Events

A baseline sign and symptom is defined as an AE that starts after the subject has provided written informed consent and that resolves prior to the first dosing occasion, or an AE that starts prior to the first dosing occasion and does not increase in severity after dosing. A treatment-emergent AE (TEAE) is defined as an AE that occurs postdose or that is present predose and becomes more severe postdose.

Nonserious AE information observed before dosing will not be listed as an AE in the eCRF but will be listed as medical history instead, unless the AE becomes more severe postdose, in which case it will be recorded as an AE in the eCRF. Serious AEs will be recorded from the time the subject signs the ICF until study completion.

All AEs will be listed. The TEAEs will be summarized by treatment, severity, and relationship to the study drug. The frequency (the number of TEAEs, the number of subjects experiencing a TEAE, and the percentage of subjects experiencing a TEAE) of TEAEs will be summarized by Medical Dictionary for Regulatory Activities (MedDRA) system organ class and preferred term. The summary and frequency TEAE tables will be presented for all causalities and for those TEAEs considered related to the study drug (those that have a relationship of at least possibly related to study treatment). Any severe or serious AEs will be tabulated. For any AEs that change

severity ratings the AE will be included only once under the maximum severity rating in the summaries.

10.4.2 Clinical Laboratory Parameters

Clinical chemistry, hematology data will be listed. In addition, all clinical chemistry panel, hematology, and UA data outside the clinical reference ranges will be listed by parameter. Any clinical chemistry, hematology, and urinalysis (UA) values outside the clinical reference ranges will be flagged on the individual subject data listings.

10.4.3 Vital Signs

The vital signs, including systolic blood pressure, diastolic blood pressure, pulse rate, and temperature data will be summarised by time point, together with changes from baseline. Figures of mean vital signs and mean change from baseline profiles will be presented by time point.

Vital signs values outside the clinical reference ranges will be flagged on the individual subject data listings. Repeat and unscheduled readings will be handled as defined in Section 10.1.2.

10.4.4 Electrocardiogram

The ECG data will be obtained directly from the 12-lead ECG traces. These data include the QT interval calculated using the Fridericia correction (QTcF), the PR and QT intervals, the QRS duration, and heart rate. The ECG data will be listed only. Values for ECG parameters outside the clinical reference ranges will be flagged on the individual subject data listings.

10.4.5 Other Assessments

All other safety assessments not detailed in this section will be listed but not summarized or statistically analysed.

10.4.6 Safety and Tolerability Statistical Methodology

No inferential statistical analyses are planned.

11. INTERIM ANALYSES

No interim statistical analyses are planned.

12. CHANGES FROM THE PROTOCOL SPECIFIED STATISTICAL ANALYSES

There were no changes from the protocol-specified statistical analyses.

13. DATA PRESENTATION

13.1 Insufficient Data for Presentation

Some of the TFLs may not have sufficient numbers of subjects or data for presentation. If this occurs, the blank TFL shell will be presented with a message printed in the center of the table, such as, “No serious adverse events occurred for this study.”

